5.1 Definition of trial periods

The trial periods are defined in [Table 1](#).

Table 1: Definition of trial periods

Trial period	Definition
Open-label phase	From the day of enrolment to the day before randomisation.
Randomised phase	From the day of randomisation to end of trial, both days included.
Maintenance phase	From the day of first exposure to maintenance IMP to the last day of exposure (rescue or maintenance IMP), both days included.
Follow-up phase	From the day after last application of maintenance or rescue IMP to end of trial.
Relapse period	Relapse is defined as a PGA score of at least 'mild' during the maintenance phase, for details on relapse see CTP section 6.14.1. A relapse period is defined from the relapse start day (included) to the

	visit date when relapse treatment is discontinued (not included).
Remission period	A remission period is a period where the subject is not in a relapse period within the maintenance phase.
Visit interval	The interval between two successive scheduled visits.

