5.5.3 Adverse Events

The adverse events (AEs) will be assigned to a specific period (e.g. open-label phase or randomised phase) based on the onset date the AE.

The long-term safety of LEO 90100 will be evaluated based on data from the randomised phase.

For treatment emergent adverse events (hereafter referred to as AEs) occurring in the randomised phase the following tables will be done:

Trial ID: LP0053-1004	Date: 15-JUL-2019	Version: 1.0 Page 31 of 177
-----------------------	-------------------	--------------------------------

An overall summary of AEs, SAEs, premature discontinuation from the trial due to AEs, treatment related AEs, severity of AEs, action taken with IMP and outcome of AEs will be presented. The summary will include number of events, number (percentage) of subjects and exposure rates.

The number of AEs, the number and percentage of subjects experiencing each type of AE, and the exposure rate will be tabulated by SOC and preferred term. The tabulation will be done for all treatment emergent AEs, for each type of severity separately, for related AEs, for serious AEs (SAEs), for non-serious adverse events, and for frequent AEs ($\geq 1\%$ in any treatment group).

All above tables will be done for the safety analysis set by treatment for the first 28 weeks of the randomised phase, and for the remaining 32 weeks of the randomised phase separately. In addition, the tables will be done for the safety analysis set by randomised treatment and rescue IMP for the total randomised phase, for the first 28 weeks of the randomised phase, and for the remaining 32 weeks of the randomised phase separately.

Further details for the tables can be found in [Appendix I](#) and [Appendix II](#).

Open-label phase:

For completeness, AEs for the open-label phase will be summarised separately as follows:

An overall summary of AEs, SAEs, AEs leading to withdrawal, treatment related AEs, severity of AEs, action taken with IMP and outcome of AEs will be presented. The summary will include number of events, number (percentage) of subjects and exposure rates.

The number of AEs, the number and percentage of subjects experiencing each type of AE, and the exposure rate will be tabulated by SOC and preferred term. The tabulation will be done for all treatment emergent AEs, for each type of severity separately, for related AEs, for serious AEs (SAEs), for non-serious adverse events, and for frequent AEs ($\geq 1\%$).

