Table 2-97 Shift tables for subject's global assessment of disease severity from start of relapse to end of relapse by visit for start of relapse: full analysis set

Figures

Figure 2-1 Estimated survival curves with 95% confidence intervals for time to first relapse: full analysis set

Figure 2-2 Estimated survival curves with 95% confidence intervals for time to first relapse: per protocol analysis set

Figure 2-3 Estimated survival curves with 95% confidence intervals for time to first relapse – sensitivity analysis: full analysis set

Figure 2-4 Distribution of proportion of days in remission: full analysis set

Figure 2-5 Distribution of proportion of days in remission: per protocol analysis set

Figure 2-6 Distribution of number of relapses during maintenance phase: full analysis set

Figure 2-7 Distribution of number of relapses during maintenance phase: per protocol analysis set

Figure 2-8 Number of days in remission between relapses: full analysis set

Trial ID: LP0053-1004	Date: 15-JUL-2019	Version: 1.0 Page 55 of 177
-----------------------	-------------------	--------------------------------

Figure 2-9 Number of days in remission between relapses: per protocol analysis set
 Figure 2-10 Stacked plot over subjects in remission by visit: full analysis set
 Figure 2-11 Stacked plot over subjects in remission by visit: per protocol analysis set
 Figure 2-12 Stacked plot for efficacy after treatment of relapse: full analysis set
 Figure 2-13 Estimated treatment difference for DLQI by visit: full analysis set
 Figure 2-14 Estimated treatment difference for PSI by week: full analysis set

Tables and Figures, Safety Data (Module 4)

Tables

Table 3-1 Overall summary of adverse events during open-label phase: open-label safety analysis set
 Table 3-2 Overall summary of adverse events during the total maintenance phase by randomised treatment: safety analysis set
 Table 3-3 Overall summary of adverse events during the first 28 weeks of the randomised phase by randomised treatment: safety analysis set
 Table 3-4 Overall summary of adverse events during the last 32 weeks of the randomised phase by randomised treatment: safety analysis set
 Table 3-5 Overall summary of adverse events during the total maintenance phase by randomised treatment and rescue medication: safety analysis set
 Table 3-6 Overall summary of adverse events during the first 28 weeks of the maintenance phase by randomised treatment and rescue medication: safety analysis set

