Severe	xxx	(xx . x)	xxx	xxx . x
Related ¹ to IMP	xxx	(xx . x)	xxx	xxx . x
Leading to withdrawal from trial	xxx	(xx . x)	xxx	xxx . x
Action taken with IMP				
Dose not changed	xxx	(xx . x)	xxx	xxx . x
Dose reduced	xxx	(xx . x)	xxx	xxx . x
Dose increased	xxx	(xx . x)	xxx	xxx . x
Drug interrupted	xxx	(xx . x)	xxx	xxx . x
Drug withdrawn	xxx	(xx . x)	xxx	xxx . x
Not applicable	xxx	(xx . x)	xxx	xxx . x
Unknown	xxx	(xx . x)	xxx	xxx . x
Outcome				
Fatal	xxx	(xx . x)	xxx	xxx . x
Not recovered/Not resolved	xxx	(xx . x)	xxx	xxx . x
Recovering/Resolving	xxx	(xx . x)	xxx	xxx . x
Recovered/Resolved	xxx	(xx . x)	xxx	xxx . x
Recovered/Resolved with sequelae	xxx	(xx . x)	xxx	xxx . x
Unknown	xxx	(xx . x)	xxx	xxx . x

AEs collected during the exposure time in the initial open-label phase are shown.

IMP: Investigational medicinal product, PYE: Patient years of exposure, N: Number of subjects with one or more events, %: Percentage of subjects with one or more events, E: Number of adverse events, R: Rate (number of adverse events divided by patient years of exposure multiplied by 100).

1) Considered possibly or probably related to trial product by the investigator.

Shell 60: Overall summary of adverse events during <XXX> by randomised treatment: safety analysis set

	LEO 90100 (n=xxx)				Vehicle (n=xxx)			
	N	(%)	E	R	N	(%)	E	R
PYE	xxx.x				xxx.x			
Events	xxx	(xx.x)	xxx	xxx.x	xxx	(xx.x)	xxx	xxx.x
Serious	xxx	(xx.x)	xxx	xxx.x	xxx	(xx.x)	xxx	xxx.x
Severity								
Mild	xxx	(xx.x)	xxx	xxx.x	xxx	(xx.x)	xxx	xxx.x
Moderate	xxx	(xx.x)	xxx	xxx.x	xxx	(xx.x)	xxx	xxx.x
Severe	xxx	(xx.x)	xxx	xxx.x	xxx	(xx.x)	xxx	xxx.x
Related ¹ to IMP	xxx	(xx.x)	xxx	xxx.x	xxx	(xx.x)	xxx	xxx.x
Leading to withdrawal from trial	xxx	(xx.x)	xxx	xxx.x	xxx	(xx.x)	xxx	xxx.x
Action taken with IMP								
Dose not changed	xxx	(xx.x)	xxx	xxx.x	xxx	(xx.x)	xxx	xxx.x
Dose reduced	xxx	(xx.x)	xxx	xxx.x	xxx	(xx.x)	xxx	xxx.x
Dose increased	xxx	(xx.x)	xxx	xxx.x	xxx	(xx.x)	xxx	xxx.x
Drug interrupted	xxx	(xx.x)	xxx	xxx.x	xxx	(xx.x)	xxx	xxx.x
Drug withdrawn	xxx	(xx.x)	xxx	xxx.x	xxx	(xx.x)	xxx	xxx.x
Not applicable	xxx	(xx.x)	xxx	xxx.x	xxx	(xx.x)	xxx	xxx.x
Unknown	xxx	(xx.x)	xxx	xxx.x	xxx	(xx.x)	xxx	xxx.x
Outcome								
Fatal	xxx	(xx.x)	xxx	xxx.x	xxx	(xx.x)	xxx	xxx.x
Not recovered/Not resolved	xxx	(xx.x)	xxx	xxx.x	xxx	(xx.x)	xxx	xxx.x
Recovering/Resolving	xxx	(xx.x)	xxx	xxx.x	xxx	(xx.x)	xxx	xxx.x
Recovered/Resolved	xxx	(xx.x)	xxx	xxx.x	xxx	(xx.x)	xxx	xxx.x

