Recovered/Resolved with sequelae	xxx	(xx.x)	xxx	xxx.x	xxx	(xx.x)	xxx	xxx.x
Unknown	xxx	(xx.x)	xxx	xxx.x	xxx	(xx.x)	xxx	xxx.x

AEs collected during the exposure time in the <total/first 28 weeks of the/remaining 24 weeks of the> maintenance phase are shown.
 IMP: Investigational medicinal product, PYE: Patient years of exposure, N: Number of subjects with one or more events, %: Percentage of subjects with one or more events, E: Number of adverse events, R: Rate (number of adverse events divided by patient years of exposure multiplied by 100).

1) Considered possibly or probably related to IMP by the investigator.

Shell 61: Overall summary of adverse events during <XXX> by randomised treatment and rescue medication: safety analysis set

	LEO 90100 remission (n=xxx)			Vehicle remission (n=xxx)			LEO 90100 relapse (n=xxx)			Vehicle relapse (n=xxx)		
	N	(%)	E	R	N	(%)	E	R	N	(%)	E	R
PYE	xxx.xx			xxx.xx			xxx.xx			xxx.xx		
Events	xxx (xx.x)	xxx	xxx.x	xxx (xx.x)	xxx	xxx.x	xxx (xx.x)	xxx	xxx.x	xxx (xx.x)	xxx	xxx.x
Serious	xxx (xx.x)	xxx	xxx.x	xxx (xx.x)	xxx	xxx.x	xxx (xx.x)	xxx	xxx.x	xxx (xx.x)	xxx	xxx.x
Severity												
Mild	xxx (xx.x)	xxx	xxx.x	xxx (xx.x)	xxx	xxx.x	xxx (xx.x)	xxx	xxx.x	xxx (xx.x)	xxx	xxx.x
Moderate	xxx (xx.x)	xxx	xxx.x	xxx (xx.x)	xxx	xxx.x	xxx (xx.x)	xxx	xxx.x	xxx (xx.x)	xxx	xxx.x
Severe	xxx (xx.x)	xxx	xxx.x	xxx (xx.x)	xxx	xxx.x	xxx (xx.x)	xxx	xxx.x	xxx (xx.x)	xxx	xxx.x
Related ¹ to IMP	xxx (xx.x)	xxx	xxx.x	xxx (xx.x)	xxx	xxx.x	xxx (xx.x)	xxx	xxx.x	xxx (xx.x)	xxx	xxx.x
Leading to withdrawal from trial	xxx (xx.x)	xxx	xxx.x	xxx (xx.x)	xxx	xxx.x	xxx (xx.x)	xxx	xxx.x	xxx (xx.x)	xxx	xxx.x
Action taken with IMP												
Dose not changed	xxx (xx.x)	xxx	xxx.x	xxx (xx.x)	xxx	xxx.x	xxx (xx.x)	xxx	xxx.x	xxx (xx.x)	xxx	xxx.x
Drug withdrawn	xxx (xx.x)	xxx	xxx.x	xxx (xx.x)	xxx	xxx.x	xxx (xx.x)	xxx	xxx.x	xxx (xx.x)	xxx	xxx.x
Not applicable	xxx (xx.x)	xxx	xxx.x	xxx (xx.x)	xxx	xxx.x	xxx (xx.x)	xxx	xxx.x	xxx (xx.x)	xxx	xxx.x
Unknown	xxx (xx.x)	xxx	xxx.x	xxx (xx.x)	xxx	xxx.x	xxx (xx.x)	xxx	xxx.x	xxx (xx.x)	xxx	xxx.x
Outcome												
Fatal	xxx (xx.x)	xxx	xxx.x	xxx (xx.x)	xxx	xxx.x	xxx (xx.x)	xxx	xxx.x	xxx (xx.x)	xxx	xxx.x
Not recovered/Not resolved	xxx (xx.x)	xxx	xxx.x	xxx (xx.x)	xxx	xxx.x	xxx (xx.x)	xxx	xxx.x	xxx (xx.x)	xxx	xxx.x
Recovering/Resolving	xxx (xx.x)	xxx	xxx.x	xxx (xx.x)	xxx	xxx.x	xxx (xx.x)	xxx	xxx.x	xxx (xx.x)	xxx	xxx.x

continued...

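### For randomised subjects, AEs dated from Visit 2 up to the first maintenance application are tabulated by arm, not as open-label; if the shell footnotes govern, some reach neither set of tables

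*SAP*

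**What the plan says.** SAP 5.1, Table 1, defines the open-label phase as "From the day of enrolment to the day before randomisation" and the randomised phase as "From the day of randomisation to end of trial, both days included". The maintenance phase is a third period: it begins only at the first exposure to maintenance product. SAP 5.5.3 assigns AEs to a period "based on the onset date the AE" and adds: "The long-term safety of LEO 90100 will be evaluated based on data from the randomised phase".

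The table templates use a different window. By-arm Shells 60, 63 and 66 carry the footnote "AEs collected during the exposure time in the <total/first 28 weeks of the/remaining 24 weeks of the> maintenance phase are shown", and the title of Table 3-2 is "Overall summary of adverse events during the total maintenance phase by randomised treatment: safety analysis set". The companion Table 3-4 is titled "Overall summary of adverse events during the last 32 weeks of the randomised phase by randomised treatment: safety analysis set". The open-label shells carry "AEs collected during the exposure time in the initial open-label phase are shown".

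Under Protocol 6.1.3 and 10.2, randomisation takes place at Visit 2, and blinded product is handed over there only if treatment success is shown. Protocol 6.1.4 lets subjects choose two fixed application weekdays, 3 or 4 days apart, settled at Visit 2.

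**The concern.** Calcium and albumin, urine calcium:creatinine and, in the HPA subset, cortisol are sampled at Visit 2 after four weeks of once-daily open-label LEO 90100. Protocol 8.12.1 and 8.12.2 require clinically significant abnormalities to be recorded as AEs. If such an AE is dated to Visit 2, it enters the by-arm tables although it reflects open-label treatment. The same holds for any AE that starts after Visit 2 but before maintenance product is first applied.

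The SAP then treats one visit in two ways. SAP 5.5.7 and 5.5.9 summarise the Visit 2 values as the end of the open-label phase, and 5.3.1 makes Visit 2 the maintenance baseline. A raised calcium could therefore appear as an open-label shift and also as an AE under vehicle in a subject who had not yet applied vehicle. At stake are the descriptive AE counts and rates in the tables on which long-term safety is to be judged, and the completeness of the open-label tables.

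**Working it through.** **Placement.** Let R be the Visit 2 date of a randomised subject. Protocol 9.2 describes start and stop dates for AEs, with no clock time. The treatment-emergent rule in Protocol 11.3.6.1 is anchored on the first application of any IP, so it does not remove these events.

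| AE onset date | Text of SAP 5.1 and 5.5.3 | Shell footnotes |
|---|---|---|
| Before R | Open-label | Open-label |
| R, maintenance dosing starts on R | Arm | Arm |
| R, maintenance dosing starts later | Arm | Neither |
| After R, before first maintenance application | Arm | Neither |
| On or after a later first maintenance application | Arm | Arm |

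In rows three and four no maintenance product had been used. In row two, a finding from a Visit 2 sample reflects open-label treatment; other same-day events cannot be timed.

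**Do the footnotes belong to other tables?** SAP 5.5.3 also plans additional maintenance-phase summaries split 28 and 24 weeks. In Appendix I, however, the AE tables split by randomised treatment alone are titled as randomised phase, except Table 3-2. The maintenance-phase AE tables otherwise use the separate layout with rescue medication. Shells 60, 63 and 66 therefore serve randomised-phase tables under a maintenance-phase footnote. The weeks show the mismatch: 28 + 24 = 52 in the footnote, 28 + 32 = 60 in the text.

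**How often the gap arises.** If the Visit 2 weekday is unrelated to the two chosen weekdays and the first dose waits for the next chosen day (assumption), dosing starts on R for 2/7 = 29% of subjects and one to three days later for 5/7 = 71%. Because the days are settled at Visit 2 itself, the true share could lie anywhere from 0 to 100%.

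**Size per event.** The plan gives no figure to reproduce.

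- Randomised subjects, SAP Table 8: 132 + 55 + 52 + 68 + 56 + 68 + 114 = 545.
- Open-label patient-years, taking the 48% success proportion in Protocol 11.1 and 28 days each: 545/0.48 = 1135 treated; 1135 × 28/365.25 = 87.0. One event is 100/87.0 = 1.15 per 100 patient-years.
- If 40% were randomised: 1363 treated, 104.5 patient-years, 0.96. If 60%: 908 treated, 69.6 patient-years, 1.44.
- One arm: 545/2 = 272.5 subjects. With 30% exponential drop-out over 52 weeks (Protocol 11.1), the mean exposed fraction is 0.30/(−ln 0.70) = 0.841, giving 272.5 × 0.841 × 364/365.25 = 228.4 patient-years. One event is 100/228.4 = 0.44.
- With no drop-out: 271.6 patient-years, 0.37. With 60%: 177.8 patient-years, 0.56.

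**Number of events.** This cannot be derived. Purely as illustration, if 0.5% to 2% of randomised subjects had such an AE (an assumption without support in the documents), that is 545 × 0.005 = 2.7 to 545 × 0.02 = 10.9, or about 3 to 11 events.

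**The case against.** The strongest reply is that the cut is the protocol's own. Protocol 11 starts the maintenance phase at randomisation, and 11.3.6.1 tabulates AEs by start date with Visit 2 as a border. Any cut by calendar day misplaces something. This stands in part: the date rule is objective, and moving it wholesale past Visit 2 would put some post-dose events under open-label. But the protocol's definition leaves no gap. The SAP moved the start of the maintenance phase to first exposure, and SAP 5.7 does not list that change.

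Few events should qualify, and that stands. Protocol Table 4 requires a physical examination at Visit 2 only for subjects who are not randomised. Protocol 9.1.1 keeps the scored perilesional signs and burning or pain out of the AE data unless serious. Central-laboratory results may well be judged after Visit 2.

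The information is also not lost. Visit 2 values are summarised as open-label, out-of-range laboratory results are listed, and all AEs are in Listing 7-5.

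A generic footnote should not override SAP 5.1 and 5.5.3. That is a fair reading, but a programmer working from the shells would follow the footnote. One could also argue that an open-label application earlier on the Visit 2 day keeps that day within open-label exposure time; Table 1 nevertheless ends that phase the day before.

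A reader might infer that every AE found at Visit 2 is misassigned. The documents do not support that: allocation is by onset date, so a finding that began earlier stays open-label. Nor does any section say whether a laboratory AE is dated by sample or by report.

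**Conclusion.** The point holds as a minor one. For randomised subjects, AEs dated on Visit 2 or in the gap before the first maintenance application go to an arm under the SAP text. Those dated before maintenance dosing starts go to no phase table under the shell footnotes.

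Per event, the open-label rate loses about 1.15 per 100 patient-years (0.96 to 1.44 for 40% to 60% randomised). Under the text one arm gains about 0.44 (0.37 to 0.56 for 0 to 60% drop-out). These figures assume that all 545 randomised subjects are in the safety analysis set and are split equally between arms.

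A reader might go further and infer a bias in the safety comparison between LEO 90100 and vehicle. The documents do not support that. Before any maintenance product is applied, such events are balanced between arms in expectation, and SAP 5.5.3 plans no AE testing. What is affected is attribution to phase and the completeness of the tables.

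**What to change.** In SAP 5.5.3, assign AEs with an onset date before the date of first maintenance application to the open-label phase. Where maintenance dosing began on the Visit 2 day, assign laboratory, urine and cortisol AEs dated to that day to open-label as well, because the samples precede dispensing. Leave other same-day AEs under the existing date rule.

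Align the footnotes of Shells 60, 63 and 66 and the title of Table 3-2 with 5.5.3: randomised phase, 28 and 32 weeks. Table 3-39, which speaks of the last 24 weeks of the randomised phase, needs the same correction. The open-label footnote in Shells 59, 62 and 65 should admit the reassigned AEs, or it would exclude them again.

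Laboratory AEs dated by report after maintenance dosing has begun should stay where their date puts them. The AE fields in Protocol 9.2 describe no link to a sample, so matching them would mean case-by-case judgement.

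The cost is a small change to the AE period derivation before unblinding, plus text edits. Patient-years are exposure-based (SAP 5.5.1), so denominators do not change. A few same-day AEs will still not be timed exactly.

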- Subjects who do not use rescue medication at Visit 15 will have a final contact (FU3) 8 weeks after Visit 15. Relapses confirmed at Visit 15 will be treated at the investigator's discretion; treatment with Enstilar[®] or IP is not allowed.
- Subjects who have completed 4 weeks of rescue treatment at Visit 15 (that is, Visit 15 is a relapse follow-up visit, see section 6.1.4.1) will have a final contact (FU3) 8 weeks after Visit 15.
- For subjects who use rescue medication at Visit 15 (that is, rescue medication was dispensed at an unscheduled visit after Visit 14 [see section 6.1.4.2]), the 8-week follow-up period will start after completion of the 4-week rescue treatment regimen (that is, at the relapse follow-up visit).

- Subjects who withdraw early from the trial, including subjects who leave the trial after the initial 4 weeks open-label treatment, will also have a follow-up visit (FU3) 8 weeks after their last IP application.

Subjects who experience rebound during the follow-up period prior to the FU3 visit will contact the site as soon as possible for an unscheduled follow-up visit (see below).

If the subject has not experienced a worsening of their psoriasis during the 8-week follow-up period, the FU3 contact may be conducted as a telephone contact, at the discretion of the investigator. If rebound is confirmed at the FU3 visit, the subject will be followed up for 14 days or until resolution (whichever occurs first). If the rebound is considered an SAE, the event must be followed up until a final outcome has been established, i.e. the follow-up may continue beyond the end of the clinical trial (see section [9.5](#)).

Rebound events in the follow-up period will be reported as (S)AEs in accordance with sections [9.2](#) and [9.4.1](#). See section [9.5](#) for the follow-up of related AEs during and after the trial.

Unscheduled follow-up visit

At the last treatment visit (Visit 15/Early Withdrawal), subjects should be instructed to contact the site if they experience a worsening of their psoriasis within the following 8 weeks to schedule a follow-up visit ('unscheduled follow-up'). The unscheduled follow-up visit should take place no more than 7 days after the initial contact.

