10.9.2.4 Drug Accountability

The investigator is fully responsible for the 0.9% Sodium Chloride Injection, USP at the trial site. Dispensing of the 0.9% Sodium Chloride Injection, USP may be delegated, e.g. to a hospital pharmacy, as locally applicable. The person responsible for dispensing the 0.9% Sodium Chloride Injection, USP will be responsible for maintaining adequate control and for documenting all transactions. All 0.9% Sodium Chloride Injection, USP sourced locally by the investigator (or designee) will be fully documented by use of (internal) drug accountability forms. An inventory will be kept of all 0.9% Sodium Chloride Injection, USP dispensed for each subject in the trial. The batch number/lot number and expiry date of the 0.9% Sodium Chloride Injection, USP dispensed will be recorded. This inventory must be available for inspection at monitoring visits and will be checked to ensure correct dispensing of the 0.9% Sodium Chloride Injection, USP.

11 Statistical Methods

The trial consists of two different periods of treatment. The subjects are enrolled in the trial at baseline. The first 4 weeks of treatment after a subject is included in the trial will be denoted the open-label treatment phase. If the subject obtains treatment success (i.e., PGA score of 'clear' or 'almost clear' with at least 2-grade improvement from baseline) at the end of the open-label treatment phase, the subject is randomised. Otherwise the subject is discontinued from the trial. The second treatment period is denoted the maintenance phase. It starts at randomisation and ends at end of trial. The randomised maintenance treatment is twice weekly treatment with either LEO 90100 aerosol foam or LEO 90100 aerosol foam vehicle. Moreover, the subjects treated twice weekly with LEO 90100 aerosol foam is referred to as the active treatment group and those treated twice weekly with vehicle is referred to as the vehicle group.

Note that the maintenance phase consists of maintenance treatment as well as periods of 4 weeks treatment with rescue medication in case of relapse.

In the following when referring to visit it means scheduled visit although not explicitly stated.

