11.3.3.3 Analysis of Primary Efficacy Endpoint

The primary endpoint is time to first relapse during the maintenance phase, where relapse is an exacerbation of psoriasis defined as a PGA of at least 'mild'. This will be calculated as the number of days from randomisation to the day where the subject has the first relapse confirmed. For subjects who either do not encounter a relapse or are withdrawn from the trial, the number of days will be treated as a censored observation at the day of end of trial visit.

The number of censored and uncensored observations, i.e. number of subjects without relapse or who are withdrawn from the trial, and number of subjects with relapse, will be summarised by treatment group. The time to first relapse will be summarised by treatment group for uncensored observations, i.e. subjects with relapse.

The primary endpoint will be compared between treatments with the null hypothesis that they are equal against the alternative that they are different. The analysis will be performed both for the full analysis set (primary) and for the per protocol analysis set (supportive). The comparison will be done using a proportional hazards model with treatment group, trial site, and disease severity at baseline (as determined by the PGA) as factors. The estimate of the hazard ratio of active treatment group relative to vehicle group together with the 95% confidence interval and p-value will be presented.

The estimated survival curves with confidence intervals will be presented graphically for each of the treatment groups. Moreover the percentiles of the survival distribution will be tabulated by treatment group.

The proportion of subjects who are still at risk for a first relapse will be compared between the two treatment groups at 26 and 52 weeks after randomisation.

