Q1;Q3	xx.x;xx.x	xx.x;xx.x
Min;Max	xx.x;xx.x	xx.x;xx.x
Visit 3-visit 4		
Number of subjects	xxx	xxx
Mean (SD)	xx.x (xx.x)	xx.x (xx.x)
Median	xx.x	xx.x
Q1;Q3	xx.x;xx.x	xx.x;xx.x
Min;Max	xx.x;xx.x	xx.x;xx.x
Visit 4		
Number of subjects	xxx	xxx
Mean (SD)	xx.x (xx.x)	xx.x (xx.x)
Median	xx.x	xx.x
Q1;Q3	xx.x;xx.x	xx.x;xx.x
Min;Max	xx.x;xx.x	xx.x;xx.x
...		
Visit 14-visit 15		
Number of subjects	xxx	xxx
Mean (SD)	xx.x (xx.x)	xx.x (xx.x)
Median	xx.x	xx.x
Q1;Q3	xx.x;xx.x	xx.x;xx.x
Min;Max	xx.x;xx.x	xx.x;xx.x
Total		
Number of relapses	xxx	xxx
Number of subjects	xxx	xxx
Mean (SD)	xx.x (xx.x)	xx.x (xx.x)
Median	xx.x	xx.x
Q1;Q3	xx.x;xx.x	xx.x;xx.x
Min;Max	xx.x;xx.x	xx.x;xx.x

SD: Standard deviation, Q1: 1st quartile, Q3: 3rd quartile

Shell 34: <xxx> by visit for end of relapse: full analysis set

Visit interval <xxx>	LEO 90100 (n=<xxx>)	Vehicle (n=<xxx>)
Visit 3-visit 4		
Number of subjects	xxx	xxx
Mean (SD)	xx.x (xx.x)	xx.x (xx.x)
Median	xx.x	xx.x
Q1;Q3	xx.x;xx.x	xx.x;xx.x
Min;Max	xx.x;xx.x	xx.x;xx.x
Visit 4		
Number of subjects	xxx	xxx
Mean (SD)	xx.x (xx.x)	xx.x (xx.x)
Median	xx.x	xx.x
Q1;Q3	xx.x;xx.x	xx.x;xx.x
Min;Max	xx.x;xx.x	xx.x;xx.x
Visit 4-visit 5		
Number of subjects	xxx	xxx
Mean (SD)	xx.x (xx.x)	xx.x (xx.x)
Median	xx.x	xx.x
Q1;Q3	xx.x;xx.x	xx.x;xx.x
Min;Max	xx.x;xx.x	xx.x;xx.x
...		
Visit 15		
Number of subjects	xxx	xxx
Mean (SD)	xx.x (xx.x)	xx.x (xx.x)
Median	xx.x	xx.x
Q1;Q3	xx.x;xx.x	xx.x;xx.x
Min;Max	xx.x;xx.x	xx.x;xx.x
Visit 15-visit X		
Number of subjects	xxx	xxx
Mean (SD)	xx.x (xx.x)	xx.x (xx.x)
Median	xx.x	xx.x
Q1;Q3	xx.x;xx.x	xx.x;xx.x
Min;Max	xx.x;xx.x	xx.x;xx.x
Total		
Number of relapses	xxx	xxx
Number of subjects	xxx	xxx
Mean (SD)	xx.x (xx.x)	xx.x (xx.x)
Median	xx.x	xx.x
Q1;Q3	xx.x;xx.x	xx.x;xx.x
Min;Max	xx.x;xx.x	xx.x;xx.x

SD: Standard deviation, Q1: 1st quartile, Q3: 3rd quartile

Shell 35: <Change / Percent change> in <xxx> from start of relapse to end of relapse by visit for start of relapse: full analysis set

Visit interval <Change / Percent change> in <xxx> from start to end of relapse period	LEO 90100 (n=xxx)	Vehicle (n=xxx)
Visit 2-visit 3		
Number of subjects	xxx	xxx
Mean (SD)	xx.x (xx.x)	xx.x (xx.x)
Median	xx.x	xx.x
Q1;Q3	xx.x;xx.x	xx.x;xx.x
Min;Max	xx.x;xx.x	xx.x;xx.x
Visit 3		
Number of subjects	xxx	xxx
Mean (SD)	xx.x (xx.x)	xx.x (xx.x)
Median	xx.x	xx.x
Q1;Q3	xx.x;xx.x	xx.x;xx.x
Min;Max	xx.x;xx.x	xx.x;xx.x
Visit 3-visit 4		
Number of subjects	xxx	xxx
Mean (SD)	xx.x (xx.x)	xx.x (xx.x)
Median	xx.x	xx.x
Q1;Q3	xx.x;xx.x	xx.x;xx.x

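### Read literally, SAP Table 1 puts a Visit 15 or early-withdrawal PGA taken after the last application outside the relapse definition, contrary to the protocol and to SAP Table 3

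*SAP*

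**What the plan says.** SAP section 5.1, Table 1 sets three definitions that work together:

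- The maintenance phase is bounded by exposure: "From the day of first exposure to maintenance IMP to the last day of exposure (rescue or maintenance IMP), both days included".
- What comes next counts as follow-up, bounded in the same way: "From the day after last application of maintenance or rescue IMP to end of trial".
- A relapse is tied to the first of these two: a "PGA score of at least 'mild' during the maintenance phase". The entry refers to a protocol section 6.14.1, which does not exist; 6.1.4.1 is presumably meant.

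The protocol draws the boundary elsewhere. The opening of section 11 says of the maintenance phase: "It starts at randomisation and ends at end of trial". Section 11.3.3.3 says that for subjects without a relapse, or withdrawn, "the number of days will be treated as a censored observation at the day of end of trial visit". Section 6.1.5 takes it that relapses can be found at the last visit: "Relapses confirmed at Visit 15 will be treated". It leaves the choice to the investigator and rules out trial product.

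The SAP is not consistent with itself. The sensitivity-analysis text in 5.4.1 right-censors at the end of the maintenance phase. Table 3, in the same section, right-censors on the day the subject completed or left the trial, and takes a relapse at a scheduled visit as confirmed on the visit day. For the primary Cox model, 5.4.1 gives no censoring date. The primary-endpoint entry in SAP 5.7 does not mention a new phase end.

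**The concern.** Maintenance product is applied on two fixed days a week, so Visit 15 will usually fall on a day after the last application. Under Table 1 such a visit belongs to follow-up, and a PGA of 'mild' or worse found there is not a relapse. The same holds for the early-withdrawal visit, where protocol Table 4 schedules a PGA.

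Visit 15 is also the planned place to confirm late relapses. Protocol 6.1.4.3 sends a relapse in the 7 days before a scheduled visit to that visit.

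Three results depend on which rule is programmed:

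- the event set for time to first relapse, and with it the exploratory at-risk proportion at week 52 (SAP 5.4.3.1);
- the secondary endpoint, number of relapses;
- the meaning of censoring at withdrawal. If a subject leaves with active disease and that relapse is not counted, the censoring is informative.

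Two programmers following the same SAP could build different event sets.

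**Working it through.** **1. The plan's own sample size.** Inputs from protocol 11.1: hazard ratio 0.7, 90% power, 5% level (two-sided, 11.3.8), 4 to 8 vehicle relapses a year, 30% exponential drop-out over 52 weeks, 1:1 allocation.

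- Events (Schoenfeld): 4 × (1.960 + 1.282)² / (ln 0.7)² = 331. Freedman's formula gives 338.
- Drop-out hazard: m = −ln(0.7)/52, median 101 weeks, as the protocol states.
- Event probability: l/(l+m) × (1 − exp(−(l+m) × 52)). Averaged over the arms it is 0.8778 at 4 a year and 0.9474 at 8 a year.
- Per group: 331/(2 × 0.8778) = 189 and 331/(2 × 0.9474) = 175. Freedman gives 193 and 179.

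The protocol's 178 to 190 is reproduced to within 3%.

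**2. How often Visit 15 falls outside the phase.** There are two application days in seven. If visit day is unrelated to them (assumption), the visit falls on an application day at most 2/7 = 29% of the time. At least 5/7 = 71% of Visit 15 dates then come after the last application.

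**3. Primary endpoint, Visit 15.** Visits 14 and 15 are 48 and 52 weeks after randomisation. First relapses arising between them are an upper bound on those first seen at Visit 15.

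| Vehicle relapses/year | Share of vehicle first relapses | Share of active first relapses | Power, all counted | Power, all of these lost |
|---|---|---|---|---|
| 4 | 0.5% | 1.2% | 90.3% (333.6 events) | 90.0% (330.7 events) |
| 8 | 0.02% | 0.15% | 92.27% | 92.25% |

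Removing events at the very end of follow-up leaves the Cox partial-likelihood terms at earlier event times unchanged, so the hazard ratio barely moves.

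**4. At-risk proportion at week 52.** If every first relapse after Visit 14 is lost, the curve stays at S(48) instead of falling to S(52), where S(t) = exp(−hazard × t). At 4 a year:

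- Vehicle (hazard 4/52): S(48) = 0.0249, S(52) = 0.0183.
- Active (0.7 × 4/52): S(48) = 0.0754, S(52) = 0.0608.
- Difference between arms: 0.0754 − 0.0249 = 0.0505, against 0.0608 − 0.0183 = 0.0425.

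At 8 a year, S(48) − S(52) is about 0.03 percentage points on vehicle and 0.2 on active.

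**5. Number of relapses.** Visit 15 is one of 13 scheduled post-randomisation PGA visits (Visits 3 to 15): 1/13 = 7.7%. This indicates scale only; it does not estimate the loss.

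**6. Early withdrawal.** The probability of leaving before a first relapse, assuming independent drop-out, is m/(l+m) × (1 − exp(−(l+m) × 52)). It is 8% (vehicle) and 11% (active) at 4 a year, and 4% and 6% at 8 a year. With 190 per arm that is about 19 to 36 of 380 subjects. This bounds the withdrawal PGAs at stake for the primary endpoint; the documents do not say how many would show 'mild' or worse.

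**The case against.** The strongest reply is that the SAP nowhere states an exclusion. Section 4 says the analysis follows the protocol, with deviations described in 5.7, and none is listed here. Table 3 treats any scheduled visit as a place where relapse can be confirmed. Shell 22 reports subjects still at risk at day 364, Visit 15. This stands: a reader might infer that Visit 15 relapses will certainly be lost, and the documents do not support that. The wording "From the day of first exposure to maintenance IMP to the last day of exposure (rescue or maintenance IMP), both days included" also keeps a visit on an application day inside the phase. Where the last application date is missing, SAP 5.5.1 substitutes the last visit date, though that rule is written for exposure.

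A reader might also take the start-of-relapse shells (33, 39, 56, 71, 77) as proof, since their last row before the total is "Visit 14-visit 15" with no Visit 15 row. The shells fit the literal reading but do not prove it. They tabulate the start of relapse periods, and a relapse confirmed at Visit 15 starts no rescue course. They are descriptive tables and do not derive the endpoints.

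On withdrawal, censoring at the end of the maintenance phase is stated only for the sensitivity analysis. Subjects withdrawn for not clearing after rescue already have a counted relapse.

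None of this removes the contradiction. Table 1 is an explicit definition, and a programmer who follows it gets an event set that the protocol does not intend.

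**Conclusion.** The point holds as a conflict between definitions. By the letter of Table 1, a PGA of 'mild' or worse at Visit 15 or early withdrawal, on a day after the last application, is not a relapse. The protocol and SAP Table 3 point the other way.

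For the primary hazard ratio and power, the Visit 15 effect is negligible under the planning assumptions. The week-52 figures (7.5% against 6.1% on active, 2.5% against 1.8% on vehicle) are upper bounds. They assume 4 relapses a year, a constant hazard, no detection at unscheduled visits in the last four weeks, and no Visit 15 on an application day. They shrink quickly at higher relapse rates. The secondary relapse count can lose some events.

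A reader might infer a general bias toward active. The documents do not establish one. The week-52 difference would widen in favour of active, but relapses lost at withdrawal could act the other way: SAP 5.7 itself allows for more withdrawals on vehicle because of lower efficacy. That component cannot be sized beyond the bound of about 19 to 36 of 380 subjects.

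**What to change.** Before unblinding:

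1. In SAP Table 1, define the relapse event separately from the relapse period. A PGA of 'mild' or worse counts for time to first relapse at any visit after randomisation up to and including Visit 15, the early-withdrawal visit, or the relapse follow-up visit if rescue runs past Visit 15. New relapses at these visits enter the number of relapses; one already counted is not counted again. Correct the cross-reference to the protocol.
2. In SAP 5.4.1, state the censoring date for the primary Cox model as the Visit 15 or early-withdrawal visit, and align the sensitivity text with Table 3. Run the risk-time offset for the number of relapses to the same visit, so that events and time at risk match.
3. Keep the exposure-based maintenance phase as it is for exposure, proportion of days in remission and adverse events. Redefining the phase itself would change the remission denominator, the imputed unobserved days, the normalisation of amount used and the assignment of adverse events.

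A Visit 15 row in the start-of-relapse shells is optional.

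The cost is a few sentences in two SAP sections and the matching derivation code. No clinical procedure changes.
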